We conducted a prospective, randomized clinical trial. Our hospital Ethics Committee (CEIm-PSMAR) approved this study (reference code: 2023/10996). Prior to patient enrollment we obtained a signed informed consent from the neonate's parents. This study was conducted according to the ethics code of the Barcelona Medical Association and the principles of the Helsinki-Fortaleza Declaration 2013, at the neonatal unit of a tertiary care hospital in Barcelona (Spain) within an area of influence of approximately 400,000 people, which experiences approximately 1,400 births per year. The target population for this study, and thus, inclusion criteria were healthy full-term neonates born at our center or less than 15 days old referred for a frenotomy, who had ankyloglossia according to the Hazelbaker tool [39] (Figure 1) between September 2023 and June 2024. We assess for the presence of ankyloglossia as part of the routine neonatal evaluation using the Hazelbaker tool to evaluate its impact on tongue movement and on breastfeeding [39]. According to the Hazelbaker tool (see Figure 1), ankyloglossia exists if appearance scores 8 points or less and/or function scores 11 points or less. We offer a frenotomy to all patients with ankyloglossia. During the study period, if we identified a patient with ankyloglossia, we offered the patient's parents the opportunity to participate in this study.

Patients were enrolled if their parents agreed to and signed a written informed consent. We only included patients who were breastfed, as after randomization we may need to get colostrum. Enrolled patients were randomized into case or control group by simple random sampling using sequentially numbered containers. During the frenotomy the neonate was taken to the neonatal unit and monitored with a pulse-oximeter (COVIDIEN Nellcor Portable SpO₂ Patient Monitoring System PM10N, Covidien Ireland Limited, [name]) before, during and after the procedure. For both groups we swaddled, administered 1 mL of oral sucrose,

and let the newborn suck for 2 minutes prior to the procedure. The control group had a 7 x 7 cm gauze pad with 1 drop (43.75 mg) of 100% pure LEO (Pranarôm España S.L.) placed 2 cm under their nose for 2 minutes prior to starting the frenotomy and for the duration of the procedure, whereas the experimental group had a gauze with 2 drops of colostrum of the patient's mother placed in the same way. We used two drops of colostrum but only one of LEO because the odor of colostrum is more subtle than that of LEO, and in our previous studies [32-33] we had used one drop of LEO, and that is how we routinely perform frenotomies. Once the procedure was completed, we removed the gauze pad and recorded vital signs, whether the baby cried or not, the seconds crying lasted, and the NIPS score on a data collection sheet. If a neonate cried, calming techniques such as holding, swaddling, and sucking were employed. A blinded observer assessed pain by means of the Neonatal Infant Pain Scale (NIPS) score (Figure 2) [40], crying duration, and whether there was a change in heart rate (HR) and/or in oxygen saturation (satO2) before and after the procedure.

In a previously published study where we compared performing frenotomies using complementary analgesia or not with inhaled LEO, we observed a mean (SD) crying time of 14.8 vs 24.6 (10.8 vs 27.6) seconds in favor of LEO [32]. In order to detect a difference of 10 seconds in crying time, we calculated that we needed a sample size of 71 patients per group in order to draw conclusions with a CI 95% and a power of 80%. We chose to evaluate pain by means of the increase of HR rather than via the NIPS score because in previous research, we obtained NIPS scores of 1.88-2.92 and 2.02-2.38, and a NIPS score less than 3 indicates no pain. We used the NIPS score to assess whether neonates exhibited pain when using inhaled colostrum instead of LEO.

We recorded demographic (sex, gestational age, birth weight, age in hours at the time of frenotomy) and clinical variables (HR and satO2 before, during, and after the

procedure, whether the patient cried or not during the procedure, length of crying time in seconds, presence of side effects during the procedure (apnea, desaturation, others) and highest NIPS score within the first 5 minutes after the procedure). The attending staff were trained to assess the NIPS score before we started recruiting patients. Even though patients were swaddled, it was feasible to feel if they moved their legs or arms. The independent variable was the use of inhaled colostrum or inhaled LEO during frenotomy. The dependent variables were HR and satO2 pre and post procedure, presence of crying and duration, hours of life at the time of the frenotomy, and the NIPS score. The controlled variables were gestational age, sex, and birth weight.

Statistical analysis: Quantitative variables (gestational age, birth weight, age at frenotomy, heart rate pre and post-procedure, increase in heart rate post-procedure, oxygen saturation pre and post-procedure, decrease in oxygen saturation post-procedure, and duration of crying) are described using the mean, standard deviation and range; experimental vs control groups were compared with a Student's t-test. We assessed the equality of variances by using Levene's test and applied the result of the Student's t-test accordingly. Sex, the presence of crying, and adverse effects between the two groups are presented in percentages and compared using Fisher's exact test. Statistical significance was set for a p <0.05. To perform statistical analyses we used STATA version 16.1 (StataCorp, College Station, TX, USA).

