Quantitative variables (gestational age, birth weight, age at frenotomy, heart rate pre and post-procedure, increase in heart rate post-procedure, oxygen saturation pre and post-procedure, decrease in oxygen saturation post-procedure, and duration of crying) are described using the mean, standard deviation and range; experimental vs control groups were compared with a Student's t-test. We assessed the equality of variances by using Levene's test and applied the result of the Student's t-test accordingly. Sex, the presence of crying, and adverse effects between the two groups are presented in percentages and compared using Fisher's exact test. Statistical significance was set for a p <0.05. To perform statistical analyses we used STATA version 16.1 (StataCorp, College Station, TX, USA).

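### No primary outcome is named: the 80% power covers crying duration only, HR increase is the chosen pain measure without any power, and at least six outcomes are tested at 0.05 with no order

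*Protocol*

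**What the plan says.** The protocol's sample size paragraph bases the trial on one variable: "In order to detect a difference of 10 seconds in crying time, we calculated that we needed a sample size of 71 patients" per group, with 95% confidence and 80% power. The planning values are means of 14.8 and 24.6 s and SDs of 10.8 and 27.6 s. Their source is introduced as "In a previously published study where we compared performing frenotomies using complementary analgesia or not with inhaled LEO", so they describe LEO against no LEO, whereas this trial compares colostrum with LEO.

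The next sentence turns to another variable: "We chose to evaluate pain by means of the increase of HR rather than via the NIPS score". No HR difference, SD or power follows. The paragraph then gives NIPS a part in judging pain as well.

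Elsewhere the outcomes appear side by side without rank. The procedure paragraph has the blinded observer assess NIPS, "crying duration, and whether there was a change in heart rate (HR) and/or in oxygen saturation (satO2) before and after the procedure". The variables paragraph says "The dependent variables were HR and satO2 pre and post procedure, presence of crying and duration", and goes on to age at frenotomy and NIPS.

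The SAP repeats the protocol's Statistical analysis paragraph. Its list for the t-test, after the baseline variables and HR before and after the procedure, ends with "increase in heart rate post-procedure, oxygen saturation pre and post-procedure, decrease in oxygen saturation post-procedure, and duration of crying". For categorical variables it says "Sex, the presence of crying, and adverse effects between the two groups are presented in percentages and compared using" Fisher's exact test. One rule covers everything: "Statistical significance was set for a p <0.05". Neither document uses the word primary, sets an order of testing or adjusts for multiple tests.

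**The concern.** A sample size normally identifies the outcome that carries the trial's conclusion. Here the sample size points to crying duration and the following sentence points to HR increase, so two careful readers could name different primary outcomes.

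Two things are at stake. First, with one threshold and no ranking, nothing in the plan prevents a significant result on any one of the outcomes from being presented as the trial's answer, and the overall false-positive rate of that reading is well above 5%. Second, the stated 80% may be taken to cover HR. A non-significant HR result can still be read through its 95% CI, but the documents give no basis for saying how well the trial could detect an HR difference.

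**Working it through.** **1. The plan's own figure.** Inputs from the protocol's sample size paragraph: difference 10 s, SDs 10.8 and 27.6, 95% confidence, 80% power. Two-sided testing and 1:1 allocation are my assumptions, as neither is stated.

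- Sum of variances: 10.8² + 27.6² = 116.64 + 761.76 = 878.40.
- Normal approximation: n = (1.960 + 0.8416)² × 878.40 / 10² = 7.849 × 8.784 = 68.9, so 69 per group.
- Unequal-variance (Welch) t-test at n = 71: SE = √(878.40/71) = 3.517, noncentrality 10/3.517 = 2.84, df 90.9, power 80.3%. At n = 70 power is 79.7%, so 71 is exactly the Welch sample size.
- A one-sided calculation gives 55, which does not match. This supports the two-sided reading.

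**2. How far the 80% carries for crying duration.** The SD in the colostrum arm is not documented. With LEO held at 10.8 and n = 71, Welch power for 10 s is:

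| Assumed colostrum SD (s) | Power |
|---|---|
| 10.8 | over 99% |
| 20 | 96% |
| 27.6 | 80% |
| 35 | 62% |

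The no-LEO SD (27.6) exceeds its mean (24.6), which suggests skew, so these powers are approximate.

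**3. HR increase.** With no difference or SD given, only standardized figures are possible (noncentral t, 71 per group, df 140).

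- 80% power needs a true difference of about 0.47 SD. Power is 66% at 0.4 SD and 43% at 0.3 SD.
- 95% CI half-width: t(0.975, 140) × √(2/71) = 1.977 × 0.168 = 0.33 SD.
- For assumed SDs of 10, 15, 20 or 25 bpm, 0.47 SD is about 4.7, 7.1, 9.4 or 11.8 bpm.

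**4. Counting the tests.** From the SAP's lists: post-procedure HR, HR increase, post-procedure satO2, satO2 decrease, crying duration and presence of crying make six. Adverse effects make seven. I leave out baseline variables, and also NIPS because no test is listed for it.

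**5. Chance of at least one false positive if all nulls are true.**

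- Independent tests: 1 − 0.95⁶ = 26.5%; with adverse effects, 1 − 0.95⁷ = 30.2%. The seventh adds little if such events are rare: the actual size of Fisher's test at 71 per group is 0.0001–0.014 for assumed rates of 1–5%.
- Six correlated tests (multivariate normal, 1,000,000 draws), equal correlation 0.3, 0.5, 0.7, 0.9: 24.1%, 20.7%, 16.4%, 10.8%.
- Three correlated pairs (HR, satO2, crying): within 0.5 and between 0.1 or 0.3, 24.8% or 23.3%; within 0.7 and between 0.1, 22.9%; within 0.9 and between 0.5, 17.0%.
- On plausible within-pair values: with equal pre and post SDs, post-procedure HR and HR increase correlate at √((1 − r)/2), where r is the pre-post correlation. That is 0.59 for r = 0.3 and 0.50 for r = 0.5.

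The correlations are assumptions, since the documents give none.

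**The case against.** The strongest reply is that crying duration is already the implicit primary outcome. It is the only variable with a target difference and a power, and in a short single-centre protocol that is a common way to signal the main endpoint. On this reading the HR sentence contrasts HR with NIPS, not with crying time, and a secondary measure needs no power calculation. The plan also never says that one significant result makes the trial positive; it only sets a threshold.

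Part of this stands. Crying duration is the most natural inference, and the misuse described is possible rather than planned. But the HR sentence follows directly on the sample size, speaks of evaluating pain and never calls HR secondary, so the ambiguity is real.

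The count can also be challenged. HR and satO2 each enter twice, and by distinct measure there are four outcomes, or five with adverse effects. Independence then gives 1 − 0.95⁴ = 18.5% or 1 − 0.95⁵ = 22.6%, and four measures at the same equal correlations give about 9–17%. Fisher's test for presence of crying is conservative (actual size 0.026–0.036 for assumed crying proportions of 0.3–0.9). That lowers the six-test independence figure to between 1 − 0.95⁵ × 0.974 = 24.6% and 1 − 0.95⁵ × 0.964 = 25.4%, so the simulated rates are slightly high. These points reduce the figure, but every version stays above 5%.

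Finally, the borrowed SD is a separate matter from the missing primary outcome, and the colostrum SDs of 20 and 35 have no source. That is fair. They show only that the 80% is conditional, and the main point does not depend on them.

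**Conclusion.** The point holds and should be corrected. No primary outcome or testing order is stated, and the 80% power belongs to crying duration alone, under SDs taken from a LEO versus no-LEO comparison. The sample size itself is correctly calculated from its inputs.

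The overall false-positive rate across six outcomes is roughly 11–25% under assumed correlations of 0.1–0.9, with 26.5% under independence. Counted as four distinct measures it is still about 9–17%. Power for HR increase is undocumented; at 71 per group it reaches 80% only for about 0.47 SD.

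**What to change.** In both the protocol and the SAP:

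- Name one primary outcome, tested at two-sided 0.05. Crying duration is the only one with a documented sample size and should be used unless the sponsor can show that another was specified beforehand.
- State that the 80% power refers to crying duration alone, for 10 s and the earlier study's LEO and no-LEO SDs.
- Label HR increase and all other outcomes secondary or exploratory, reported with 95% CIs and without confirmatory claims.
- Disclose that the primary outcome was designated post hoc, unless prior specification can be shown.

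The cost is wording only: no new data, and 71 per group is unchanged. The downside is that an isolated significant result for HR, satO2 or presence of crying could not be claimed as confirmatory. Making crying duration and HR increase co-primary at 0.025 each would cost more: crying duration would need (2.241 + 0.842)² × 878.40 / 100 = 83.5, so 84 per group, and its power at 71 would fall to 72.6% (normal approximation).

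The documents are in the past tense, with enrolment dated to June 2024, so a new label cannot by itself restore prespecification. The practical gain is that readers know which result carries the design's power and which do not.

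### Does the absence of the NIPS score from the listed analyses call for a change to the plan?

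*Protocol*

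**What the plan says.** NIPS appears in three places in the Protocol.

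- **Procedure paragraph.** It comes first among the observer's measures: "A blinded observer assessed pain by means of the Neonatal Infant Pain Scale (NIPS) score".
- **Sample size paragraph.** It is ranked below heart rate: "We chose to evaluate pain by means of the increase of HR rather than via the NIPS score". The reason given is that in earlier work "we obtained NIPS scores of 1.88-2.92 and 2.02-2.38, and a NIPS score less than 3 indicates no pain". The next sentence gives NIPS its remaining job: "We used the NIPS score to assess whether neonates exhibited pain when using inhaled colostrum instead of LEO".
- **Variables paragraph.** The recorded value is the "highest NIPS score within the first 5 minutes after the procedure", staff are trained in scoring before recruitment, and NIPS closes the list of dependent variables: "presence of crying and duration, hours of life at the time of the frenotomy, and the NIPS score".

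The Statistical analysis paragraph, repeated word for word as the SAP, has two lists. The quantitative list ends "decrease in oxygen saturation post-procedure, and duration of crying) are described using the mean, standard deviation and range", with a Student's t-test between groups. The categorical list reads "Sex, the presence of crying, and adverse effects between the two groups are presented in percentages", with Fisher's exact test. NIPS is in neither list, as a score or as a category.

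**The concern.** A variable with a stated question and a place among the dependent variables should have a stated analysis. The quantitative list looks closed: it goes down to derived quantities such as the rise in heart rate and the fall in saturation, and has no wording to suggest that these are examples. Someone who followed it literally would report heart rate, saturation and crying but nothing on the only pain scale collected. The NIPS question would then stay open whether it is read as a check on the colostrum arm or as a comparison of arms.

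The choice of summary is also left free. A mean, a median and the share of infants at 3 or more can point in different directions, and a choice made after seeing the data could favour one conclusion. The only guide to interpretation sets a cut-off of 3 beside non-integer earlier values, which could tempt a reader to take a group value below 3 as proof that no infant was in pain.

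**Working it through.** **1. Is the omission real?** Each dependent variable in the Protocol's variables paragraph, set against the analysis text:

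| Dependent variable | Stated analysis |
|---|---|
| Heart rate, pre and post | mean, SD, range; t-test |
| Oxygen saturation, pre and post | mean, SD, range; t-test |
| Presence of crying | percentages; Fisher |
| Duration of crying | mean, SD, range; t-test |
| Hours of life at frenotomy | mean, SD, range; t-test (as age at frenotomy) |
| NIPS | none |

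Five of six are covered, and NIPS is the exception. The list closes cleanly in both documents, so a PDF break does not explain it.

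**2. Does the sample size depend on NIPS?** Inputs from the sample size paragraph: difference 10 s, SDs 10.8 and 27.6 s, power 80%. A two-sided 5% level is assumed from the 95% CI.

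- Pooled SD = √((10.8² + 27.6²)/2) = √(878.4/2) = 20.96 s.
- n per group = 2 × (20.96 × (1.960 + 0.842)/10)² = 68.9, so 69 by the normal approximation.
- The pooled t version gives 70, and the unequal-variance (Satterthwaite) t version gives 71, the plan's figure.

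The 71 per group is reproduced from crying time alone.

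**3. What is already fixed for NIPS?** The assessor (blinded observer), the value per infant (highest score), the window (first five minutes) and a threshold (below 3 means no pain). Only the group-level summary and the test are missing. As a score, NIPS fits the plan's quantitative template. Split at 3, it fits the categorical one. Neither needs new data or a method outside the plan.

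**4. Can the consequence be sized?** Three calculations are possible, and none measures harm from the gap.

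- *Ceiling on the share at 3 or more.* For non-negative whole-number scores the largest possible share is mean/3: 2.92/3 = 97% and 1.88/3 = 63%. This assumes that 2.92 and 1.88 are means, which the Protocol does not say. It also needs every infant in pain to score exactly 3 and every other infant 0.
- *Precision of a share.* With 71 per arm the exact 95% interval is 0 to 5.1% for 0/71, and 4.1 to 19.3% for 7/71.
- *Precision of a difference.* At an assumed 20% in both arms the half-width is 1.96 × √(2 × 0.2 × 0.8/71) = 0.132, or 13.2 points. Over assumed rates of 10% to 50% it runs from 9.9 to 16.4 points.

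The last two hold for any yes/no outcome with 71 per arm. They would be the same had NIPS been listed.

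**The case for a change.** The best case for a change is that the repair is small and uses the Protocol's own score, window and cut-off. A secondary outcome line with a per-arm summary and an interval for the difference would answer both readings of the NIPS question and close off a choice of summary after the fact. Nor does the heart-rate preference dispose of NIPS, because the very next sentence gives NIPS a separate purpose.

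Part of this stands. The lists do omit NIPS, and even a descriptive summary is not named. The caution on interpretation is also sound: a group value below 3 does not show that each infant was free of pain, and a non-significant test would not show equal pain.

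The rest is weaker. A descriptive check against 3 is the natural reading of a sentence that directly follows the threshold, so it is too strong to say that the plan would yield nothing on NIPS. Which summary to write in is itself open: one statistician would split at 3 and accept the loss of information, another would analyse the ordinal score with a median or rank method. The gain from fixing it in advance is also doubtful. Both documents are in the past tense and the recruitment window was September 2023 to June 2024, so wording added now might count only as post hoc. The documents do not say whether outcomes had been seen.

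**Conclusion.** No change is needed. The gap is genuine but is one of completeness: one supporting variable out of six dependent variables is missing from the analysis lists. No stated rule gives a wrong result. The heart-rate and crying analyses, which carry the preferred pain measure and the sample size, stand as written.

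This rests on two judgements. The first is that an analyst holding a blinded, defined and collected dependent variable will tabulate it by arm and compare it with one of the plan's two existing methods. The second is that NIPS is secondary, which follows from the Protocol's preference for heart-rate increase and its use of crying time for the sample size. No size can be put on the consequence, because the documents give no NIPS spread, target difference or share at 3 or more.

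### Side effects are recorded only during the procedure, although odor exposure starts 2 minutes earlier, so apnea, other reactions and transient desaturations outside that window do not enter the Fisher comparison

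*Protocol*

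**What the plan says.** The Protocol's procedure paragraph has the gauze, with LEO or colostrum, "placed 2 cm under their nose for 2 minutes prior to starting the frenotomy and for the duration of the procedure". It ends the exposure at completion: "Once the procedure was completed, we removed the gauze pad and recorded vital signs". That paragraph goes on to list crying and NIPS among the items recorded at this point, but not side effects.

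The paragraph on recorded variables sets the observation windows. Heart rate and saturation have the widest: "clinical variables (HR and satO2 before, during, and after the" procedure. The list then ends with "presence of side effects during the procedure (apnea, desaturation, others) and highest NIPS score within the first 5 minutes after the procedure". Pulse-oximeter monitoring is described as taking place "before, during and after the procedure".

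The Protocol's statistical analysis paragraph and the SAP, which are worded alike, compare adverse effects between groups as percentages with Fisher's exact test. They give no time window and no event definitions. They also compare satO2 before and after the procedure, and its decrease, by t-test.

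**The concern.** The randomized difference between the groups is the inhaled product, and exposure to it begins 2 minutes before the cut. The only written rule for side effects covers the procedure itself. A neonate who becomes apneic during those 2 minutes, or shortly after the gauze is taken away, has no recorded side effect under that rule. Other variables in the same list have windows that extend before or after the procedure, so the narrower wording for side effects reads as a limit and not as loose phrasing.

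At stake is what the adverse-effect comparison can support. A report that few or no side effects occurred with either product would cover only part of the time during which infants inhaled it, and none of the time afterwards.

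**Working it through.** **1. The windows side by side (all from the Protocol)**

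| Item | Before the cut, gauze in place (2 min) | Procedure | After gauze removal |
|---|---|---|---|
| Odor exposure | yes | yes | no |
| Oximeter monitoring | yes (start relative to gauze not stated) | yes | yes |
| HR and satO2 recorded | yes (timing relative to gauze not stated) | yes | yes |
| Side effects | **no** | yes | **no** |
| NIPS, highest score | no | no | yes, 5 min |

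**2. Where different events would go, following the text as written**

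- Apnea or another reaction before the cut: outside the side-effect window, and not an HR or satO2 reading. It is not counted.
- Apnea or another reaction after gauze removal: not counted, for the same reason.
- A desaturation after removal that is absent at the post-procedure reading: not counted as an event and not visible in the satO2 change.
- A saturation fall still present at the post-procedure reading: enters the post value and the decrease, which are compared as means. The planned description includes the range, so an extreme value would show. It is still not an event in Fisher's test.
- A saturation fall before the cut: its handling depends on when the baseline is read. If the baseline is taken after gauze placement, an exposure-related fall sits in the baseline and makes the later decrease look smaller.

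Readings during the procedure are recorded, but the analysis list names only pre, post and change values.

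**3. The plan's own figure**

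The only design figure is 71 per group, for a 10-second difference in crying time with SDs of 10.8 and 27.6 s, 80% power and a 0.05 significance level (taken as two-sided).

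- SD = √[(10.8² + 27.6²)/2] = √439.2 = 20.96 s.
- n = 2 × (1.960 + 0.842)² × 439.2 / 10² ≈ 69 per group. The observed difference of 9.8 s gives 72, and the t-based versions give 70 and 73.

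The stated 71 reproduces. It does not depend on the side-effect window and serves below only as the denominator.

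**4. What 71 per group means for the Fisher comparison (illustration)**

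- With no events in one group, two-sided p = 2 × C(71,k)/C(142,k) for k events in the other. For k = 5, p = 0.058. For k = 6, p = 0.028.
- Six against none is therefore the least that reaches p < 0.05 when one group has no events. If one of those six fell outside the window, the result would move to five against none and lose significance.
- With no events in 71, the one-sided 95% upper limit is 1 − 0.05^(1/71) = 4.1%. The figure is the same whatever the window, but the statement covers only the window in which events were counted.

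**5. Number of missed events**

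This would be 71 per group multiplied by the probability of an event occurring only outside the window. The documents give no event rate, so the product cannot be computed.

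**The case against.** The strongest reply is that the Protocol never defines the procedure and uses its time words loosely, so staff may have counted the gauze period. The analysis text puts no time limit on adverse effects, and the data sheet is not shown. This is possible, but the procedure paragraph places the 2 gauze minutes before the start of the frenotomy. If staff did read the rule differently, the endpoint was applied unevenly and needs the same definition.

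It is also fair to say that side effects are not among the listed dependent variables, that the trial was sized for crying time, and that nothing in the documents suggests a wider window would change a conclusion. That limits the weight of the point but does not remove it, because a between-group test of adverse effects is planned.

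Four stronger readings are tempting, and the documents do not support them:

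- *Reactions outside the procedure are absent from the safety data altogether.* They are not: satO2 before and after, and its decrease, are compared between groups.
- *Most of the exposure is uncounted.* If the frenotomy lasted 10 to 60 s, the uncounted share would be 120/130 = 92% to 120/180 = 67% of exposure time. The duration is an assumption, and a share of time is not a share of missed events.
- *Events before the cut must be due to the odor, while counted events are confounded by the cut.* Before the procedure all infants also receive sucrose, are swaddled and suck, so a single event could have those causes. Both groups have the frenotomy as well, so it does not bias the between-group comparison.
- *The missing data already exist.* Infants were monitored, but nothing says that oximeter traces were stored.

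**Conclusion.** The point holds as a defect in the recording window. As written, apnea, other reactions and transient desaturations before the cut or after gauze removal do not enter the Fisher comparison of adverse effects. A saturation fall that persists to the post-procedure reading is partly captured as a change in means.

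The number of events lost is unknown and cannot be derived from the documents. The conclusion assumes that the procedure means the frenotomy, as the gauze instruction implies, and that the adverse effects in the analysis text are the side effects in the variable list. The sample size and the crying-time comparison are untouched. The change is worth making because it is cheap and because the adverse-effect comparison would then cover the whole randomized exposure.

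**What to change.** - Define the side-effect window in the Protocol as running from gauze placement to 5 minutes after the procedure, which is the end of the existing NIPS window.
- On the data sheet, code each event as before the cut, during the procedure, or after gauze removal.
- State whether the baseline HR and satO2 reading is taken before or after the gauze is placed.
- In the SAP, apply Fisher's exact test to the whole window and list events by period.
- The documents are written in the past tense. If data were already collected under the narrower window, say so and limit any safety statement to that window.

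The cost is one more data-sheet item and a few sentences in the Protocol and SAP. Infants are already monitored before, during and after the procedure and scored for NIPS over the 5 minutes after it, and the sample size does not change. A small downside is that the reported event rate may be slightly higher.

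### Gestational age, sex and birth weight are called controlled without stratification or adjustment, and age at frenotomy and pre-procedure readings are classed as outcomes

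*Protocol*

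**What the plan says.** The Protocol's paragraph on recorded variables assigns roles. It states "The controlled variables were gestational age, sex, and birth weight", and it also states "The dependent variables were HR and satO2 pre and post procedure, presence of crying and duration, hours of life at the time of the frenotomy", followed by the NIPS score. Earlier in the same paragraph, age is grouped differently: "We recorded demographic (sex, gestational age, birth weight, age in hours at the time of frenotomy".

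On design, the Protocol says "Enrolled patients were randomized into case or control group by simple random sampling using sequentially numbered containers". No stratification, blocking or minimisation is mentioned. Eligibility covers "healthy full-term neonates born at our center or less than 15 days old referred for a frenotomy".

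On analysis, the SAP and the Protocol's statistical analysis paragraph carry the same text. The list to be compared begins "Quantitative variables (gestational age, birth weight, age at frenotomy, heart rate pre and post-procedure" and goes on to the outcomes. For all of them, "experimental vs control groups were compared with a Student's t-test", with Levene's test deciding the variance assumption. Sex, presence of crying and adverse effects are compared with Fisher's exact test. Neither document names a model, covariate, stratum or subgroup.

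**The concern.** Two labels do not match what is planned.

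First, calling a variable controlled tells the reader that the design or the analysis has dealt with it. Here the three variables appear in the analysis only as items tested between arms, in the same list as the outcomes.

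Second, a dependent variable is one that the intervention might change. The gauze is placed 2 minutes before the procedure, so the odour cannot affect the infant's age, or an HR or saturation reading taken before the odour starts. These are baseline characteristics. Age may matter, because eligibility mixes infants born at the centre with infants referred up to 15 days of age, yet it enters no outcome comparison as a covariate.

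At stake are the accuracy of the stated methods, protection against chance imbalance in this particular trial, and precision for crying duration, the outcome behind the sample size.

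**Working it through.** **Inputs from the Protocol.** Target difference in crying time 10 s; SDs from the sponsor's earlier study 10.8 and 27.6 s; 71 per group; 80% power; significance at p < 0.05. A two-sided test and 1:1 allocation are assumed, as neither is stated.

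**1. The plan's own sample size.**
- Root-mean-square SD = √((10.8² + 27.6²)/2) = √439.2 = 20.96 s.
- n per group = (1.96 + 0.84)² × (10.8² + 27.6²)/10² = 68.9, so 69.
- The unequal-variance t calculation (Satterthwaite degrees of freedom) gives exactly 71.

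The stated 71 is therefore reproduced with no covariate term. The trial was sized for an unadjusted comparison.

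**2. Chance imbalance in one baseline variable.**
- SD of the standardised difference = √(2/71) = 0.168.
- 95% of chance differences lie within ±1.96 × 0.168 = ±0.33 SD.
- P(|difference| > 0.25 SD) = 2 × [1 − Φ(0.25/0.168)] = 13.6%.

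**3. What an imbalance does to crying time.** Shift = correlation × imbalance × 20.96 s. The documents give no correlation between any covariate and crying, so 0.1 to 0.45 is an assumed range.
- Imbalance 0.25 SD: 0.5 s (0.1 × 0.25 × 20.96) to 2.4 s (0.45 × 0.25 × 20.96).
- Imbalance 0.33 SD: 0.7 s to 3.1 s.
- For scale, the standard error of the difference is 20.96 × √(2/71) = 3.5 s and the target is 10 s.

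**4. Validity of the unadjusted t-test.** This was checked in 40,000 simulated trials per setting, with 71 per arm, one skewed covariate and no treatment effect.

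| Assumed correlation | Type I error, all trials | Type I error, imbalance above 0.33 SD |
|---|---|---|
| 0.224 | 0.050 | 0.069 |
| 0.316 | 0.049 | 0.099 |
| 0.447 | 0.049 | 0.149 |

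The test holds its level overall. It is unreliable only in the minority of trials (about 5%) where the imbalance is that large and the covariate is prognostic.

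**5. Precision from adjustment.** The residual SD becomes 20.96 × √(1 − R²), where R² is the share of crying-time variance explained by the covariates (assumed). Power at 71 per group for 10 s = Φ(10/(3.52 × √(1 − R²)) − 1.96).

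| R² | Power | n per group for 80% power |
|---|---|---|
| 0 | 81.1% | 69 |
| 0.05 | 83.1% | 66 |
| 0.10 | 85.0% | 63 |
| 0.20 | 88.9% | 56 |

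Adjustment would not call for more than the planned 71 per group.

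**The case against.** The strongest reply is that this is mostly labelling. Randomisation balances covariates in expectation, an unadjusted comparison of randomised arms is valid, and adjustment is an option rather than a requirement. No link between these covariates and crying or HR is documented. Even a 0.25 SD imbalance would shift the result by less than one standard error under the assumed correlations. All of that stands, and it limits the point.

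Several stronger readings are tempting but not supported:

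- **That nothing at all controls the three variables.** Full-term eligibility restricts gestational age. What is missing is stratification or adjustment; sex and birth weight have no stated restriction either.
- **That age is ignored.** Age at frenotomy is t-tested between arms. It is absent only as a covariate.
- **That a chance difference in age would be reported as an effect of the odour.** Neither document says so, and the analysis list places age beside gestational age and birth weight, as a baseline table would.
- **That ages run from the first hours of life to 15 days.** The upper limit is worded for referred infants and no lower limit is given. The low end is inferred from age being recorded in hours.
- **That an imbalance in at least one of several covariates is close to a coin toss.** For four variables, 1 − (1 − 0.136)⁴ = 44%, but this needs independence, and gestational age and birth weight are plausibly correlated. The 0.25 SD threshold is also a convention.

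One caution bears on the remedy. The Protocol notes that colostrum may have to be collected after randomisation, so allocation could slightly alter when the frenotomy takes place. Age at frenotomy is then not strictly a baseline variable; age at randomisation is.

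**Conclusion.** The point holds in a limited form. Beyond randomisation and the full-term restriction, the stated control is not delivered by stratification or adjustment. The Protocol contradicts itself on whether age is demographic or dependent, and pre-procedure HR and saturation are misclassified in the same way.

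This does not invalidate the planned tests or the sample size. The cost is an inaccurate statement of method, about a 14% chance per covariate of an imbalance above 0.25 SD, and a possible loss of precision: nothing if R² is 0, about 2 percentage points of power at 0.05 and about 8 at 0.20. The imbalance figure assumes 71 per arm and a normal approximation. The precision figures rest on assumed R² values, and how prognostic the covariates are is unknown from these documents. The change is worth making because it costs almost nothing, not because the trial fails without it.

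**What to change.** 1. In the Protocol's paragraph on recorded variables, move age at frenotomy and pre-procedure HR and saturation to the baseline variables. State that between-arm tests of baseline variables will not be read as outcome results.
2. In both documents, specify a linear model with robust standard errors for crying duration and for post-procedure HR (or HR increase). Include arm, age in hours, gestational age, sex and birth weight, and add pre-procedure HR to the HR model. Use age at randomisation if it can be obtained; the Protocol lists only age at frenotomy as recorded.
3. Report the unadjusted t-test alongside.
4. The Protocol is written in the past tense. If the data have already been seen, keep the t-test as the main analysis, label the adjusted model as supportive, and describe gestational age, sex and birth weight as described at baseline rather than controlled.

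The cost is some rewording, one regression per outcome, and four or five degrees of freedom out of 142 − 2 = 140. Apart from age at randomisation, every covariate is already collected, and 71 per group remains sufficient.
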